## 1.0 OBJECTIVES

### 1.1 Primary Objective

To assess the feasibility of single-fraction radiotherapy to provide a short-interval treatment response in patients with MESCC, such that radiographic decompression is achieved, or additional stereotactic radiotherapy to full therapeutic doses can be delivered while respecting spinal cord constraints, based on the following metrics:

- Shortest distance between gross disease and the spinal cord before and after treatment
- Epidural tumor volume before and after treatment
- Extent of epidural compression before and after treatment

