### 3. Primary Endpoint

The primary endpoint of this study is the radiographic response of the spinal tumor, as measured by:

Distance between the gross disease and spinal cord  $\geq$  3mm after treatment.

A reduction in the epidural tumor volume or thecal sac compression by  $\geq$  10% after treatment

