### 5.3 Target Volumes and Coverage

Image fusion between MRI (gadolinium contrast T1-weighted and T2-weighted images) and simulation CT is recommended for delineation of both the soft tissue tumor

component and the spinal cord. If possible, CT myelogram should be obtained prior to simulation for accurate delineation of the true cord. Special attention (and consideration of deformable registration) should be taken with image fusion when simulation CT and MRI images are taken in different imaging positions.

The gross tumor volume (GTV) should include only the gross disease visible on pre-treatment imaging. A 0-3mm margin expansion is allowed to clinical target volume (CTV), as well as a further 1-2 mm expansion to planning target volume (PTV).

For 3D treatment, the target volume should also be delineated. The treatment field can include a margin of 1-2 cm beyond the vertebral body(s) in any direction, based on the treating physician's discretion, as long as more than or equal to 90% of the target spine volume is covered by the prescription dose.

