## 6.0 RESPONSE ASSESSMENT

### 6.1 Primary Endpoint – Radiographic Response

The primary endpoint of this study is achieving radiographic response in the metastatic spinal lesion.

Radiographic response will be achieving 3mm in shortest distance axially between the gross disease and spinal cord at the level where the most severe compression was present, between pre-treatment and interval imaging scans.

Radiographic response will also be achieving a 10% reduction in epidural tumor volume or thecal sac compression between pre-treatment and interval imaging scans. Epidural tumor volume will be estimated by using target volumes contoured before and after treatment by the same practitioner. Thecal sac compression will be estimated using a method adapted from [12]. The thecal sac area at the level of compression is compared to the average value of thecal sacs measured at 1 vertebral body above and below this level. One minus the ratio of the compressed to normal thecal sac area will provide an estimate of the thecal sac compression. These measurements will be taken at the same spine levels to maintain consistency.

Response assessments will be completed by an attending radiation oncologist not directly involved in the patient's clinical care. This approach will preserve objectivity and mirrors an existing peer review process in place for all standard and stereotactic radiation treatments. Collaboration with neuroradiology will also be encouraged during these assessments.

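### Section 6.1 takes epidural tumor volume from radiotherapy target volumes, none of which is defined as epidural; used whole, they make the volume arm of the 10% criterion measure something else

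*Combined protocol and SAP*

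**What the plan says.** Three places name the epidural part of the tumor as the quantity of interest.

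- Section 1.1 lists "Epidural tumor volume before and after treatment" among the metrics of the primary objective.
- The Primary Endpoint section (numbered 3, between 4.2 and 4.4) asks for "A reduction in the epidural tumor volume or thecal sac compression by" 10% or more.
- Section 6.1 states: "Radiographic response will also be achieving a 10% reduction in epidural tumor volume or thecal sac compression between pre-treatment and interval imaging scans".

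The only instruction for obtaining the volume is the next sentence of Section 6.1: "Epidural tumor volume will be estimated by using target volumes contoured before and after treatment by the same practitioner".

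The target volumes are defined in Section 5.3. For the GTV: "The gross tumor volume (GTV) should include only the gross disease visible on pre-treatment imaging". A margin of 0–3 mm may be added for the CTV, and a further 1–2 mm for the PTV. A separate line covers the other technique: "For 3D treatment, the target volume should also be delineated". What that 3D target contains is not stated.

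The same paragraph of Section 6.1 specifies the other arm of the criterion, thecal sac compression, in detail: reference levels, a formula, and the same spine levels at both times.

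**The concern.** The named quantity and the named source do not match. The GTV is visible gross disease wherever it lies. Section 3.1 admits sites involving up to three contiguous vertebral bodies, so gross disease can extend well beyond the canal. The CTV and PTV add margins that are not tumor. Section 6.1 does not say which target volume applies, whether it is cropped to the canal, or what is contoured after treatment when no second fraction is planned. The second fraction is discretionary under Sections 4.1, 4.2 and 5.1.

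Two assessors could both follow the text and classify the same patient differently. If the volumes are used whole, the error can go either way: a real epidural response can be diluted below 10%, or a fall elsewhere can be counted as an epidural response. The 10% criterion is met by volume or thecal sac compression. The thecal sac arm can therefore rescue a missed volume response, but it cannot overrule a false one.

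**Working it through.** The plan does not derive the 10% threshold from anything, so there is no figure of its own to reproduce. The check asks what a whole-target measurement would read.

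**Inputs from the documents.** The threshold is 10% (Primary Endpoint section; Section 6.1). The CTV margin is 0–3 mm and the PTV margin a further 1–2 mm, so at most 5 mm in total (Section 5.3).

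**Inputs assumed, because the documents do not give them.** The epidural share of the GTV is f. Targets are spheres of 5 to 100 cc.

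**1. GTV used whole.** If the epidural part falls by e and the rest by b,

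measured fall = f·e + (1 − f)·b.

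With b = 0, a reading of 10% needs e = 0.10/f. With e = 0, it needs b = 0.10/(1 − f).

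| f | Reading when the true epidural fall is 10% and b = 0 | Epidural fall needed to read 10% (b = 0) | Fall elsewhere that reads 10% with no epidural change |
|---|---|---|---|
| 1.0 | 10% | 10% | not applicable |
| 0.5 | 5% | 0.10/0.5 = 20% | 0.10/0.5 = 20% |
| 0.3 | 3% | 0.10/0.3 = 33% | 0.10/0.7 = 14% |
| 0.2 | 2% | 0.10/0.2 = 50% | 0.10/0.8 = 12.5% |

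**2. CTV or PTV used, with a different margin at the two times and an unchanged tumor.** For a sphere of radius r = (3V/4π)^(1/3) and total margin m₁ before and m₂ after,

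apparent fall = 1 − ((r + m₂)/(r + m₁))³.

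| GTV | r | Margin 1 mm → 0 mm | Margin 5 mm → 4 mm |
|---|---|---|---|
| 5 cc | 10.61 mm | 1 − (10.61/11.61)³ = 23.7% | 1 − (14.61/15.61)³ = 18.0% |
| 30 cc | 19.28 mm | 1 − (19.28/20.28)³ = 14.1% | 1 − (23.28/24.28)³ = 11.9% |
| 100 cc | 28.79 mm | 1 − (28.79/29.79)³ = 9.7% | 1 − (32.79/33.79)³ = 8.6% |

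A 1 mm difference therefore reads as roughly 9% to 24%. It exceeds the threshold for small and medium targets and falls just short of it at 100 cc.

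**3. CTV or PTV used, with the same margin both times.** If the GTV falls by 10%,

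measured fall = 1 − ((r·0.9^(1/3) + m)/(r + m))³.

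With m = 5 mm this is 6.9% at 5 cc and 8.6% at 100 cc. With m = 1 mm it is 9.2% and 9.7%. A constant margin therefore also pulls a 10% change below the line, though by less.

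**4. What does not use target volumes.** The thecal sac measure is one minus a ratio of areas (Section 6.1). The treatment effect in Section 7.1 is the proportion reaching at least 3 mm between gross disease and cord. Neither depends on these contours.

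**The case against.** A reader might infer that the 10% criterion certainly measures the wrong quantity. The text does not go that far. Estimating a volume by using a contour could mean taking only the part of it that lies in the canal, and all three definitions call the quantity epidural. What the documents show is an undefined measurement that would be wrong if the target volumes are taken whole. That limits the wording of the point but does not remove it, because no cropping rule is given.

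The margin argument is conditional as well. The GTV carries no margin and is the natural choice for a tumor volume. Section 6.1 compares scans rather than treatment plans, and one practitioner draws both contours. Margins matter only if CTV or PTV is used, which the text leaves open. Section 5.3 does not say whether margins may differ between time points. The figures depend on assumed size, and the effect is smaller for large targets.

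The dilution figures rest on an assumed f and on unchanged non-epidural disease. No section states either.

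A reader might also infer that the whole radiographic endpoint fails. It does not: one arm of an either/or criterion is affected. The 3 mm proportion is the only quantity given a confidence interval and the only one used to size the next study, and it is untouched. No hypothesis is tested.

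Nor should the argument lean on the 64% epidural reduction quoted in Section 2.3. That was seen at 2 months and this trial's interval scan is at 14–21 days, so timing alone limits the comparison. The documents plan no such comparison.

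**Conclusion.** The point holds in conditional form. Section 6.1 names a source, and the target volumes defined in Section 5.3 do not yield epidural volume unless an unstated step is added. Used whole, with other disease unchanged, they raise the epidural fall needed for response from 10% to 20–50% for f between 0.5 and 0.2. If other disease shrinks, response can be declared with no epidural change. If CTV or PTV were used, a 1 mm margin difference would be about as large as the threshold itself. All these sizes depend on assumptions about f, target size and behavior outside the canal that the documents do not settle.

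The consequence is limited to the volume arm of the 10% criterion in a descriptive pilot. It should be corrected because it is part of the stated primary endpoint and cannot be measured reproducibly as written. It does not undermine the analysis in Section 7.1.

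**What to change.** Replace the sentence on epidural volume in Section 6.1 with wording such as:

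> Epidural tumor volume is a dedicated contour of tumor within the spinal canal, without CTV or PTV margin, drawn by the same practitioner on the pre-treatment and interval diagnostic scans (same modality) over the same craniocaudal extent. GTV, CTV and PTV are not used for response.

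With f = 1 and no margin, a 10% epidural fall then reads as 10%. The rule should be in place before any scan is read for response.

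The cost is one extra contour on each of two scans already in the study calendar, with no new scan or visit. Section 4.1 already requires the interval scan to use the same modality as diagnosis. Section 3.1 allows CT myelogram or diagnostic CT as well as MRI, so the contouring rule has to be workable on each. The documents give no basis for estimating the contouring time.

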### 6.2 Secondary Endpoints – NRPS, FACT-G, Ambulation

Secondary endpoints include pain, quality of life and functional outcomes.

For evaluation of pain relief, the Numerical Rating Pain Scale will be used, as done in RTOG 0631. The NRPS is a measure of pain on an 11-point scale (0-10) and has been validated previously on similar cohorts [16].

For quality of life, the Functional Assessment of Cancer Therapy (FACT-G), v. 4.0, also will be collected (also utilized in RTOG 0631). The FACT-G is a commonly used tool measuring quality of life from 4 different perspectives (physical, social, emotional and functional) [17]. It is completed quickly, is accessible to those with varying educational backgrounds, and is available in many languages ([http://www.facit.org/translation/translation\\_landing.aspx](http://www.facit.org/translation/translation_landing.aspx)).

Functional outcomes and ambulation will be assessed by standard neurologic assessment (Appendix D) by the treating physician.

## 7.0 STATISTICAL CONSIDERATIONS

### 7.1 Data Analysis

This pilot study will yield preliminary data on the primary endpoint of distance between gross disease and spinal cord of at least 3mm. Data from the study will be summarized using standard descriptive statistics; formal hypothesis testing will not be performed. Estimates of the treatment effect and standard error on the number of subjects achieving  $\geq 3$  mm distance will also be used to determine the sample size required for the larger scale study. Therefore, the size of the pilot study should be sufficient to produce reasonably precise estimates of these parameters, where precision is measured by the width of the 95% confidence interval.

The treatment effect will be estimated by  $p$ , the observed proportion of patients achieving at least 3 mm distance from the gross disease and spinal cord. Confidence intervals for the true proportion will be computed using Clopper-Pearson exact confidence interval. With 24 subjects and assuming an expected response rate  $p = 50\%$  produces a two-sided 95% confidence interval with a width equal to 58% (i.e.  $21\% \leq p \leq 79\%$  ). The width shows that the response rate will not be lower than 20%. Since this is a feasibility, study no power calculation is done.

Data regarding secondary endpoints will be reported in a descriptive manner.

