# Adaptive Staged SBRT for Spinal Metastases

## SCHEMA

Sample size: 15 patients

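### The sample size is 15 in the schema and 24 in Section 7.1, and the printed 95% interval (21% to 79%, width 58%) fits neither; the 20% floor drawn from it does not follow.

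*Combined protocol and SAP*

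**What the plan says.** The schema states "Sample size: 15 patients". Section 7.1 (Data Analysis) uses another number: "With 24 subjects and assuming an expected response rate" of 50%, the plan "produces a two-sided 95% confidence interval with a width equal to 58" percent, with limits of 21% and 79%. The method is named in the same paragraph: "Confidence intervals for the true proportion will be computed using Clopper-Pearson exact confidence interval".

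Section 7.1 also sets the criterion for the pilot's size. The size should give reasonably precise estimates, and "precision is measured by the width of the 95% confidence interval". It excludes formal hypothesis testing and says that "no power calculation is done", so interval width is the only support for the sample size. The observed proportion and its standard error are then to be used to size a larger study.

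The sentence after the interval draws a conclusion from it: "The width shows that the response rate will not be lower than 20" percent.

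**The concern.** Three things look wrong.

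1. **Two sample sizes.** The schema and Section 7.1 differ by nine patients. No text explains the gap as enrolled versus evaluable patients, a dropout allowance or replacement.
2. **An interval too wide for 24 patients.** A 95% interval for a proportion of one half is widest in small samples, and 58 points suggests a sample of about a dozen.
3. **A floor taken from a planning interval.** The 21% to 79% interval assumes that exactly half the patients respond. It sets no limit on what the trial will observe or on the true rate.

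At stake are when enrolment ends, whether the stated precision describes the study being run, and whether someone planning the larger study takes 20% as an established minimum response rate.

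**Working it through.** **Inputs.** Sample size 15 (schema) or 24 (Section 7.1). Section 7.1 also gives the expected response rate of 50%, the two-sided 95% level, the Clopper-Pearson method, the stated limits of 21% and 79%, and the stated width of 58%.

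**Formula.** For x responders among n patients:

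- lower limit = 2.5% quantile of Beta(x, n − x + 1)
- upper limit = 97.5% quantile of Beta(x + 1, n − x)

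**Step 1: try to reproduce the plan's figure.** With n = 24 and x = 12, the limits are the 2.5% quantile of Beta(12, 13) and the 97.5% quantile of Beta(13, 12). They are 29.1% and 70.9%, a width of 41.8 points. The printed width is larger by 58 − 41.8 = 16.2 points, so rounding does not explain it.

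Other methods do not recover it. At n = 24 and 50%, the 95% widths are 37 points (Wilson, Agresti-Coull), 38 (Jeffreys), 40 (Wald) and 44 (Wald with continuity correction). A Clopper-Pearson interval near 21% to 79% at n = 24 would need a confidence level between 99.5% (22% to 78%) and 99.8% (20% to 80%).

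**Step 2: the schema's size and the size that fits.** Half of 15 is not a whole number, so both neighbouring counts are shown.

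| Responders / n | 95% Clopper-Pearson interval | Width (points) |
|---|---|---|
| Printed in Section 7.1 | 21% to 79% | 58 |
| 12/24 | 29.1% to 70.9% | 41.8 |
| 7/15 | 21.3% to 73.4% | 52.1 |
| 8/15 | 26.6% to 78.7% | 52.1 |
| 6/12 | 21.1% to 78.9% | 57.8 |

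With the response rate set at 50%, every n from 8 to 30 was tried under the named method. Only n = 12 rounds to both printed limits and the printed width. Its neighbours do not: n = 11 gives 20% to 80% (width 60) and n = 13 gives 22% to 78% (width 56).

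**Step 3: the 20% floor.** The lower limit depends on the count observed. The largest counts that leave it below 20% are:

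- n = 15: 6 responders (lower limit 16.3%); 7 responders give 21.3%.
- n = 24: 9 responders (lower limit 18.8%); 10 responders give 22.1%.

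If the true rate is the assumed 50%, the chance of such a result is a binomial tail:

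- n = 15: P(X ≤ 6) = 9,949 / 32,768 = 0.304
- n = 24: P(X ≤ 9) = 2,579,130 / 16,777,216 = 0.154

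If the true rate were 40% (an assumption for illustration, not a figure in the plan), the same tails are 0.61 and 0.49.

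**Step 4: what the choice of size changes downstream.** The standard error at 50% is √(0.25/n): √(0.25/15) = 12.9 points, or √(0.25/24) = 10.2 points. The input to the larger study therefore depends on which size applies.

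**The case against.** The strongest defence is that the width error is harmless. At either stated size the correct interval is narrower than the printed one (52 or 42 points against 58), so the pilot is more precise than the plan claims. The plan sets no numerical threshold for adequate precision, so none is missed. The larger study will be sized from the observed proportion and its standard error, and the planning width does not enter that calculation. All of this stands.

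It can also be said that the origin of the printed figure is not certain, and that is right. Twelve appears nowhere in the documents as a sample size. At n = 15, a Wald interval with continuity correction gives 21.4% to 78.6%, which rounds to the printed limits, although its width is 57.3 points. Pairing the lower limit for 7/15 with the upper limit for 8/15 gives 21.3% to 78.7%. The first is not the named method and the second is not an interval for any single result. The match with 6/12 is therefore an inference from arithmetic; the failure at 24 and at 15 under the named method is not.

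Last, the floor sentence might be read as conditional on observing about 50%. On that reading it survives correction, since 29.1% and 21.3% both exceed 20%. No decision rule uses 20%. But the sentence as written carries no condition and speaks of the response rate itself, so it overstates certainty.

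None of these points settles whether the trial enrols 15 or 24.

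**Conclusion.** The concern holds. The two sample sizes are contradictory and unreconciled. The printed interval is wrong for both under the plan's own method: the width should be 41.8 points at 24 patients, or 52.1 points at 15. The claim that the response rate will not be below 20% is a false inference; at a true rate of 50% the lower limit falls below 20% with probability 0.30 at 15 patients and 0.15 at 24.

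The interval results rest on the stated method, the two-sided 95% level and a response at or next to 50%. The probabilities also assume independent patients who are all evaluable. The width error is in the conservative direction. The point must still be corrected, because this calculation is the only justification of the pilot's size and the accrual target cannot be read from the plan.

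**What to change.** State one sample size in the schema and in Section 7.1, then make the precision statement match it.

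- **If 15:** *With 15 patients and 7 or 8 responders, the 95% Clopper-Pearson interval is 21% to 73% or 27% to 79%, a width of 52 points.*
- **If 24:** *With 24 patients and 12 responders, the 95% Clopper-Pearson interval is 29% to 71%, a width of 42 points.*

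Delete the sentence on the 20% floor. If a statement about 20% is wanted, make it conditional on the count: the lower 95% limit exceeds 20% if at least 7 of 15 patients respond, or at least 10 of 24.

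If the two numbers were meant as different quantities, such as evaluable and enrolled patients, say so and base the interval on the number analysed.

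**Cost.** With 15, this is a wording amendment to Section 7.1 alone. With 24, the schema changes as well and the accrual target is 24 − 15 = 9 patients above the one it now shows. The choice is the sponsor's; the corrected arithmetic does not itself call for more patients.

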## 8.0 REGULATORY CONSIDERATIONS

### 8.1 Protection of Human Subjects

The Investigator must ensure that patients or their legally acceptable representatives are clearly and fully informed about the purpose, potential risks and other critical issues regarding clinical trials in which they volunteer to participate. Preparation of the consent form is the responsibility of the Investigator and must include all elements required by CFR 21 Part 50.25 and the local IRB.

### 8.2 Compliance with the Protocol and Protocol Revisions

The study must be conducted as described in this approved protocol. All revisions to the protocol must be provided to the PI. The PI should not implement any deviation or change to the protocol without prior review and documented approval/favorable opinion from the IRB/IEC of an Amendment, except where necessary to eliminate an immediate hazard(s) to study patients.

The investigator must ensure that patients or their legally acceptable representatives are clearly and fully informed about the purpose, potential risks and other critical issues regarding clinical trials in which they volunteer to participate. Preparation of the consent form is the responsibility of the PI.

## 9.0 DATA HANDLING AND RECORD KEEPING

### 9.1 Confidentiality

Information about study subjects will be kept confidential and managed according to the requirements of the Health Insurance Portability and Accountability Act of 1996 (HIPAA). Those regulations require a signed subject authorization informing the subject of the following:

What protected health information (PHI) will be collected from subjects in this study

Who will have access to that information and why

Who will use or disclose that information

The rights of a research subject to revoke their authorization for use of their PHI.

In the event that a subject revokes authorization to collect or use PHI, the investigator, by regulation, retains the ability to use all information collected prior to the revocation of subject authorization. For subjects that have revoked authorization to collect or use PHI, attempts should be made to obtain permission to collect at least vital status (i.e. that the subject is alive) at the end of their scheduled study period.

